#### **8.1.2 150 mg Tablets**

Fostamatinib 150 mg tablets are supplied as orange film coated, plain, oval, biconvex tablets. Each tablet contains 150 mg of fostamatinib and the inactive ingredients of the tablet core are mannitol, sodium bicarbonate, sodium starch glycolate, povidone, magnesium stearate. The inactive ingredients of the film coating are polyvinyl alcohol, titanium dioxide, polyethylene glycol 3350, talc, iron oxide (yellow), and iron oxide (red).

Matching placebo tablets containing magnesium stearate, microcrystalline cellulose and lactose monohydrate. The inactive ingredients of the film coating are polyvinyl alcohol, titanium dioxide, polyethylene glycol 3350, talc, iron oxide (yellow), and iron oxide (red) are supplied.

### **8.2 Storage**

Supplies of fostamatinib and placebo tablets will be stored at the study sites in a secure location with restricted access at room temperature (below 30°C) with temperature monitoring.

### **8.3 How Supplied/Study Drug Dispensation**

Fostamatinib and matching placebo are supplied in white opaque HDPE bottles capped with white polypropylene child resistant closures with foil induction seals.

- At Week 0/Baseline, subjects will be randomized via the RTSM system. Two bottles of assigned study drug should be dispensed. The first dose of study drug should be administered in the clinic to ensure that the subject understands dosing instructions
- At the monthly visits (Weeks 4, 8, 12, 16, 20), subjects will be instructed to bring any open bottles containing any unused study drug for accountability. Study drug will be

dispensed to cover dosing until the next visit. Subjects may keep a back up bottle for the duration of the study or until the dose is changed.

- In the event a subject loses a bottle or does not have enough study drug to last until the next monthly visit, one extra bottle of study medication may be dispensed.
- At Week 24, the final bottles dispensed will be collected and reviewed for drug accountability. Any remaining bottles previously dispensed to the subject and not previously collected (such as those dispensed at unscheduled visits or for dose modifications) will be collected for final drug accountability.

Eligible subjects enrolling in the open label extension study will be dispensed a separate supply not used in this study via the RTSM system.

#### **8.4 Study Drug Administration**

For bid dosing, subjects will self-administer one tablet twice daily by mouth: once in the morning and once in the evening, at least 8 hours apart. For *qd* dosing, subjects will self-administer one tablet daily by mouth in the morning. Subjects should be instructed that, if they miss a dose, they should take the next dose at the normal time and should not take two doses at the same time to make up for the missed dose.

Tablets may be taken with or without food. In the event of gastric upset, it may be useful to take tablets with food.

#### **8.5 Emergency Unblinding**

In the event of a medical emergency, when management of a subject's condition requires knowledge of the study drug, the subject's treatment assignment may be unblinded to disclose the identity of the study drug dispensed. Investigators will utilize the RTSM if unblinding is considered warranted. The RTSM will record the reason for unblinding, the name of the user account that performed the unblinding, and the date and time of the unblinding on the unblinding confirmation. Unblinding should only be performed if it will affect the way the subject would be treated.

#### **8.6 Study Drug Accountability/Drug Compliance**

The Investigator will be responsible for monitoring the receipt, storage, dispensation, and accountability of all study drug according to accepted medical and pharmaceutical practice. All documentation of study drug shipments must be retained by the site. Accurate, original site records of study drug inventory and dispensation must be maintained. All records must be made available to the Sponsor (or designee) and appropriate regulatory agencies upon request.

Study drug is manufactured, packaged and labelled in accordance with the principles and guidelines of cGMPs (Directive 2003/94/EC). Treatment compliance will be monitored via study documentation including patient records and drug accountability logs.

The study Pharmacy Manual provides detailed instructions regarding the preparation and handling of study drug.

## 9.0 ADVERSE EVENTS

### 9.1 Definitions

**Adverse Event (AE):** An AE is any untoward medical occurrence in a subject administered a pharmaceutical product and which does not necessarily have a causal relationship with this treatment. An AE can therefore be any unfavorable and unintended sign (including an abnormal laboratory finding, for example), symptom, or disease temporally associated with the use of an investigational study drug, whether or not considered related to the study drug.

Changes in hemoglobin that meet the study criteria for clinical significance (protocol [Section 7.13.4](#)) should be captured as adverse events.

**AEs may include, but are not limited to:**

- Subjective or objective symptoms spontaneously offered by the subject and/or identified by the investigator or study staff, including laboratory abnormalities of clinical significance;
- AEs not previously observed in the subject that emerge during the protocol-specified AE reporting period, including signs or symptoms associated with the target disease that were not present before the AE reporting period; and
- Complications that occur as a result of protocol-mandated interventions such as a venipuncture.

**The following are generally NOT considered an AE:**

- Pre-Existing Condition: A pre-existing condition (documented on the medical history eCRF) is not considered an AE unless the severity, frequency, or character of the event worsens during the study period; or
- Diagnostic Testing and Procedures: Testing and procedures should not be reported as AEs or SAEs, but, rather, the cause for the test or procedure should be reported.

**Assessment of Severity:** Refer to CTCAE criteria version 5.0 November 27, 2017 as guidance for grading of adverse events. If the event is not listed within CTCAE categories or judged as CTCAE greater than Grade 3, then the intensity of an event should be evaluated as referred to below:

- Grade 1 (Mild) – asymptomatic or mild symptoms; clinical or diagnostic observations only; intervention not indicated.
- Grade 2 (Moderate) – minimal, local or noninvasive intervention indicated;
- Grade 3 (Severe) – severe or medically significant but not immediately life-threatening; hospitalization or prolongation of hospitalization indicated; disabling; age-appropriate, instrumental activities of daily life are limited.

- Grade 4 – Life threatening consequences; urgent intervention indicated; self-care activities of daily life are limited.
- Grade 5 – Death related to AE.

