#### 4.4 Safety Endpoints

The following safety endpoints will be evaluated:

- Incidence and severity of treatment-emergent adverse events (TEAEs)
- Incidence and severity of TEAEs of Interest
- Change from Baseline for select laboratory tests over time (e.g., hematology, chemistry)
- Change from Baseline in blood pressure over time
- Change from Baseline in absolute neutrophil count (ANC) over time
- Change from Baseline in liver function tests (i.e., alanine aminotransferase [ALT], aspartate aminotransferase [AST]), total bilirubin, direct and indirect bilirubin) over time.

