#### **10.3.9.1 Treatment-Emergent Adverse Events and TEAE of Interest**

Treatment-emergent adverse events will be coded according to MedDRA. TEAEs are defined as events that first occurred or worsened following first dose of study treatment administration. All adverse events recorded as occurring before study treatment administration will be considered Baseline conditions. Related TEAEs are events considered related to study treatment by the investigator (i.e., possibly related, probably related, or related).

The number of events, the number of subjects, and the percentage of subjects who experienced at least one TEAE, incidence rate adjusting exposure will be presented. In addition, TEAEs that are considered by the Investigator to be related to a study drug; TEAEs that lead to early withdrawals; and serious TEAEs will be summarized in the same manner. Frequent TEAEs, including preferred terms with an incidence rate of  $\geq 5\%$  and TEAEs of interest will also be summarized. TEAEs of interest include hypertension, neutropenia, gastrointestinal complaints (nausea, vomiting, diarrhea, and abdominal pain, both overall and separately), infection, and liver function test elevation.

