### **10.3.9.3 Change from Baseline in Laboratory Values**

For selected hematology and chemistry laboratory tests performed, change from Baseline will be calculated for each subject and study visit. Box plots indicating mean and median as well as the 25th and 75th percentiles, and/or spaghetti plots will be presented by treatment group and study visit for both raw values and changes from Baseline.

Summary statistics (i.e., mean, median, standard deviation, maximum, and minimum, 25th and 75th percentiles) for the actual values, changes from Baseline, and maximum value observed post treatment will be tabulated by treatment group and study week. In addition, shifts based on lab values classified per CTCAE criteria V 5.0 at Baseline (i.e., Study Week 0), the maximum grade observed, and the grade observed for the last value post Baseline will be tabulated. New Grade 3 CTCAE on treatment in selected laboratory results will be listed.

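### Section 9.1 sends adverse events judged above CTCAE Grade 3 to a generic scale without laboratory thresholds, so an asymptomatic laboratory event may be recorded at a lower grade than a milder CTCAE Grade 3 event

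*Combined protocol and SAP*

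**What the plan says.** Section 9.1, under Assessment of Severity, opens with "Refer to CTCAE criteria version 5.0 November 27, 2017 as guidance for grading of adverse events". It then sets two triggers for a fallback scale. If an event is "not listed within CTCAE categories or judged as CTCAE greater than Grade 3, then the intensity of an event should be evaluated" on the five grades listed there. The relevant fallback grades are:

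- Grade 1: "asymptomatic or mild symptoms; clinical or diagnostic observations only; intervention not indicated"
- Grade 3: "severe or medically significant but not immediately life-threatening; hospitalization or prolongation of hospitalization indicated", with disability and limits on daily activities also named
- Grade 4: "Life threatening consequences; urgent intervention indicated; self-care activities of daily life are limited"

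None of the five grades refers to a laboratory value. No other section says that a listed event above CTCAE Grade 3 keeps that grade for adverse event reporting.

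Section 4.4 makes incidence and severity the first safety endpoint for all TEAEs and the second for TEAEs of interest. Under Section 10.3.9.1, "TEAEs of interest include hypertension, neutropenia, gastrointestinal complaints", infection and liver function test elevation. Laboratory values take a separate route: Section 10.3.9.3 tabulates "shifts based on lab values classified per CTCAE criteria V 5.0 at Baseline" against the maximum and last post-baseline grades. Sections 10.3.9.5 and 10.3.9.7 use CTC grades for ANC, and for ALT, AST and total bilirubin.

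**The concern.** A fallback scale is needed where CTCAE has no entry for a term. The second trigger covers events that CTCAE has already graded, and only the most severe of them. For a clinical event with life-threatening consequences it changes nothing, because the fallback Grade 4 gives the same answer. It can matter for a laboratory event placed above Grade 3 by its value, in a subject without symptoms. There the value no longer counts and the grade depends on symptoms, intervention and function.

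At stake is the ordering at the top of the severity scale for two TEAEs of interest defined largely by laboratory results, neutropenia and liver test elevation. The ITP experience in the protocol places these events mainly on fostamatinib. The same event could also carry one grade in the adverse event data and another in the laboratory shift tables, and sites could differ in how they grade similar values.

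**Working it through.** The plan gives no figure to reproduce. The first part is a reading of the rule; the second is a rough count.

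**Applying the rule.** Take two asymptomatic laboratory adverse events of the same kind, both listed in CTCAE: A at CTCAE Grade 3, and B above Grade 3.

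1. *Can an asymptomatic value be an adverse event?* Yes. Section 7.13.4 accepts a result that the investigator or sponsor considers to be one, without requiring a symptom.
2. *Event A* is listed and is not above Grade 3. Neither trigger applies, so it stays at Grade 3.
3. *Event B* meets the second trigger and goes to the fallback scale:

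| Fallback grade | Does asymptomatic event B fit? | Order relative to A (Grade 3) |
|---|---|---|
| 4 | Only if the investigator judges the consequences life-threatening; the value alone does not meet the wording | Kept |
| 3 | Possible, as medically significant | Lost (tie) |
| 2 | Possible, if a minor intervention is indicated | Inverted |
| 1 | Only if no intervention is indicated | Inverted |

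4. *Direction.* Short of death, which is Grade 5 on the fallback scale, a CTCAE Grade 4 event can only keep its grade or lose it.
5. *Does Appendix 2 narrow the choice?* In part. It calls for interrupting study drug when AST or ALT is 5 x ULN or higher with total bilirubin below 2 x ULN, and when ANC is below 1.0 x 10^9/L and still low after 72 hours. Grade 1 then fits poorly. Grade 2 is not ruled out.
6. *Laboratory tables.* Sections 10.3.9.3, 10.3.9.5 and 10.3.9.7 grade results directly, so B keeps its CTCAE grade there whatever the adverse event form says.

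**Expected number of events.** Inputs: 45 fostamatinib subjects (Section 10.1). Table 1, fostamatinib N=102, Severe column: neutropenia 1%, ALT increased 0%, AST increased 0%. The placebo total is 0% for all three.

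- Expected subjects = n x rate. Neutropenia: 45 x 0.01 = 0.45. ALT or AST: 45 x 0 = 0.
- Let s be the share of severe events above CTCAE Grade 3. The documents do not give s. Over s = 0 to 1, the expected number is 0.45 x s = 0 to 0.45.
- At the upper end (s = 1), P(none) = 0.99^45 = 0.636; P(exactly one) = 45 x 0.01 x 0.99^44 = 0.289; P(two or more) = 1 - 0.636 - 0.289 = 0.075.
- Median ITP exposure was 86 days (Section 3.6.2), against 24 weeks = 168 days here. If risk grew in proportion to time (an assumption), the upper end becomes 0.45 x 168/86 = 0.88, still under one subject.

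The protocol's larger ITP rates count a different thing. Neutropenia of any severity at 6% (Table 1) to 7% (Section 3.6.2.4) gives 45 x 0.06 = 2.7 to 45 x 0.07 = 3.15 subjects. ALT/AST above 3 x ULN at 9% (Section 3.6.2.2) gives 45 x 0.09 = 4.05. These are subjects with the event at all, not subjects whose event would reach the second trigger.

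**The case against.** The strongest reply is that the rule leaves room for sound grading and that the laboratory signal does not depend on it. CTCAE is offered as guidance and the fallback is worded as a recommendation. The fallback is broader than a symptom scale: it covers intervention, hospitalization, medical significance and daily function, and has its own Grades 4 and 5. An investigator facing an extreme neutrophil or transaminase value can choose Grade 3 as medically significant. Grading is blinded (Section 5.7). The shift tables show extreme values by arm under CTCAE whatever the adverse event grade, and the summaries of related, serious and withdrawal TEAEs do not use the grade.

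Most of this stands. A reader might infer that such events must fall to Grade 1, or that the adverse event and laboratory tables will necessarily disagree. The documents support neither. A reader might also take the 3 and 4 subjects from the any-severity rates as the number affected; Table 1's Severe column shows that they are not.

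Two points remain. Discretion does not repair the rule: two sites can follow it and grade the same value differently, and one of them can place it below a milder event. The shift tables preserve the laboratory finding, but they do not correct the TEAE severity endpoint in Section 4.4, which rests on the adverse event grade.

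**Conclusion.** The concern holds as a fault in a stated rule with a small expected effect. The second trigger in Section 9.1 allows a listed laboratory event above CTCAE Grade 3 to be recorded below a milder Grade 3 event, and allows its adverse event grade to differ from its laboratory grade. It does not require either result.

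On the ITP severe rates the likely number of affected fostamatinib subjects is zero or one (expected 0 to 0.45). The effect is confined to adverse event severity reporting. It would be an overreading to see a threat to the efficacy analyses, alpha, power or sample size; none of these uses the grade.

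Assumptions:

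- CTCAE v5.0 assigns grades above 3 to some laboratory results by value. The documents show that laboratory values are graded by CTCAE but do not print the thresholds.
- ITP rates carry over to wAIHA. The grading scale behind Table 1 is not stated, and its rates are rounded.
- The count covers only neutropenia and transaminases, not other laboratory events.
- Section 10.3.9.1 does not describe a table by grade; that severity will be reported is taken from Section 4.4.

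**What to change.** In Section 9.1, delete the part of the sentence that sends events judged above CTCAE Grade 3 to the fallback scale. State that every CTCAE-listed event, including Grades 4 and 5, is graded by CTCAE v5.0, and that the generic scale is used only for terms CTCAE does not list. Before database lock, query the recorded severity of any adverse event linked to a laboratory value above CTCAE Grade 3.

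The cost is one deleted clause and, on the counts above, very few queries. The downside is that small amount of query work. No dosing or clinical management rule has to change.

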**Serious Adverse Event (SAE):**

Note: The terms “severe” and “serious” are not synonymous. Severity (or intensity) refers to the grade of an AE (see below). “Serious” is a regulatory definition.

A serious adverse event (experience) or reaction is any untoward medical occurrence that at any dose:

- Results in death;
- Is life-threatening. (With regards to determining if an AE is serious, “life-threatening” is defined as an AE in which the subject was at risk of death at the time of the event. It does not refer to an event which hypothetically might have caused death if it were more severe. If either the investigator or the Sponsor believes that an AE meets the definition of life threatening, it will be considered life-threatening);
- Requires in-patient hospitalization or prolongation of an existing hospitalization;
- Results in persistent or significant disability/incapacity (e.g., the AE results in substantial disruption of the subject’s ability to conduct normal life functions); or
- Is a congenital anomaly/birth defect;
- Is considered an important medical event (or medically significant) that may not result in any of the above outcomes but based upon appropriate medical judgment, may jeopardize the subject and may require medical or surgical intervention to prevent one of the outcomes listed

Medical and scientific judgment should be exercised in deciding whether other situations, such as important medical events, should also be considered serious. Some examples of such events are intensive treatment in an emergency room or at home for allergic bronchospasm; blood dyscrasias, or convulsions that do not result in hospitalization; or development of drug dependency or drug abuse. Given that the investigator’s perspective may be informed by having actually observed the event and Rigel is likely to have broader knowledge of the study drug and its effects to inform its evaluation of the significance of the event, if either Rigel or the investigator believes that the event is medically significant, the event will be considered as such or an important medical event in the absence of other seriousness criteria.

The following hospitalizations are NOT considered an SAE:

**Pre-Planned Hospitalization:** A hospitalization planned prior to signing the ICF is not considered an SAE but rather a therapeutic intervention. However, if during the pre-planned hospitalization an event occurs which prolongs the hospitalization or meets any other SAE criteria, the event

will be considered an SAE. Surgeries or interventions that were under consideration but not performed prior to initiation of treatment in the study will not be considered as SAEs if they are performed after initiation of treatment in the study for a condition that has not changed from its baseline level. Hospitalizations for social or administrative reasons, due to long travel distances, or emergency room admissions of less than 24 hours are also not considered SAEs.

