### 3.6.2.1 Hypertension

Increased BP, including the development of hypertension, has been reported in patients treated with fostamatinib. Hypertensive crisis occurred in 1% of ITP patients. Patients with preexisting hypertension may be more susceptible to the hypertensive effects of fostamatinib.

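### Section 9.1 excludes emergency room stays under 24 hours from SAE status without keeping the other seriousness criteria in force, so a literal reading could lose or delay an SAE report

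*Combined protocol and SAP*

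**What the plan says.** All the relevant wording is in protocol Section 9.1.

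- **Criteria.** The SAE definition lists six alternatives: death, life-threatening, in-patient hospitalization or its prolongation, disability, congenital anomaly, and important medical event. A life-threatening event "is defined as an AE in which the subject was at risk of death at the time of the event". An important medical event is one that "may jeopardize the subject and may require medical or surgical intervention to prevent one of the outcomes listed".
- **Examples.** To illustrate where judgment may make an event serious, the section names "intensive treatment in an emergency room or at home for allergic bronchospasm; blood dyscrasias, or convulsions that do not result in hospitalization".
- **Either-party rules.** If the investigator or the sponsor considers an event life-threatening, it is treated as such. The same holds for medical significance.
- **Exclusions.** A list introduced by "The following hospitalizations are NOT considered an SAE" covers pre-planned admissions first and ends by stating that "emergency room admissions of less than 24 hours are also not considered SAEs". Social and administrative admissions are in the same sentence.
- **Override.** For pre-planned admissions only, SAE status is restored "if during the pre-planned hospitalization an event occurs which prolongs the hospitalization or meets any other SAE criteria".

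**The concern.** One part of Section 9.1 decides seriousness by what happened to the subject. The closing sentence of the exclusion list decides it by where the subject was treated and for how long. For an event managed in an emergency room and discharged within a day, the two can give opposite answers, and the text does not say which prevails. A site that sees an override attached to pre-planned admissions and none attached to emergency room admissions may reasonably conclude that the difference is deliberate.

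Several things depend on SAE status:

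- the investigator's 24-hour report, and the telephone call for fatal or life-threatening cases (Section 9.2.3);
- the sponsor's expedited assessment and its aggregate review of SAEs against control (Section 9.3);
- the summary of serious TEAEs (Section 10.3.9.1).

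An event classed as non-serious on the strength of the exclusion would miss all of these.

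**Working it through.** The plan states no figure on this point and no arithmetic applies. The check is to set the sentences side by side and see for which events they disagree.

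1. **Which criteria depend on a hospital stay?** Of the six, only the hospitalization criterion does. The other five can be met with no admission at all, and any one of the six is enough.

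2. **Do the examples confirm this?** Yes. They include emergency room or home treatment, and events that explicitly do not lead to hospitalization. Length of stay is not mentioned.

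3. **What does the exclusion sentence deny?** It denies SAE status, not hospitalization status. Had it said only that a short emergency room stay is not an in-patient admission, it would have switched off one criterion and left five standing.

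4. **Is there an override?** The one that exists is tied to events occurring during a pre-planned hospitalization. The later sentence on social or administrative, long-travel and emergency room admissions has no equivalent.

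5. **Apply both rules to an event treated in an emergency room.**

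| Situation | Six criteria | Exclusion read literally | Conflict? |
|---|---|---|---|
| Under 24 hours, no other criterion met | Not serious | Not an SAE | No |
| Under 24 hours, subject at risk of death | Serious | Not an SAE | Yes |
| Under 24 hours, judged an important medical event | Serious | Not an SAE | Yes |
| 24 hours or longer | Decided by the criteria | Does not apply | No |

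The conflict is therefore confined to short stays for events that are serious on a criterion other than hospitalization. The protocol's own bronchospasm example falls there if the stay is under 24 hours and the event is judged important.

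6. **What survives a misclassification?** Section 9.2.2 requires every AE to go on the AE eCRF, whether serious or not. What is lost is the serious flag and whatever follows from it.

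**The case against.** The strongest reply is that the sentence classifies admissions, not medical events. Its heading concerns hospitalizations, and Section 9.1 says elsewhere that the cause of a test or procedure is what gets reported, not the procedure. On that reading a short emergency room stay merely fails the in-patient criterion and the rest of the definition is untouched. The either-party rules point the same way, since the sponsor or the investigator alone can make an event life-threatening or medically significant.

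Other routes also make such events visible. Section 7.9 calls for rescue to be discussed with the Medical Monitor, beforehand where possible. Section 7.13.4 requires a laboratory abnormality that meets SAE criteria to be reported as one. Hypertension is a TEAE of interest (Section 10.3.9.1), TEAEs leading to interruption or discontinuation are listed (Section 10.3.9.2), and a DMC reviews safety data (Section 10.5).

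Most of this stands. The narrow reading is probably what was meant, and the event itself would not disappear. It does not remove the defect, because the operative words deny SAE status and nothing says the either-party rules prevail over the later exclusion. Those rules are also a weaker safeguard in real time: the sponsor's prompt notice is normally the SAE form, which is what a literal reader would not send.

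A reader might go further and infer that hypertensive crises or acute hemolysis will go unreported at a calculable rate. Section 3.6.2.1 says "Hypertensive crisis occurred in 1% of ITP patients". In 45 fostamatinib subjects that gives 45 × 0.01 = 0.45 expected events and a chance of 1 − 0.99^45 = 36% of at least one. But this is the chance of any crisis, carried over from another disease. It is not the chance of one that is treated in under 24 hours, serious on another criterion, and then misclassified. Nor is every such event automatically serious: Appendix 2 defines hypertensive crisis by blood pressure values, and transfusion is a permitted rescue in Section 7.9, not a seriousness criterion. The documents give no rate for acute hemolysis and do not say how often either event is handled in a short emergency room stay.

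**Conclusion.** The point holds as a wording conflict within Section 9.1 that bears on safety reporting. Read literally, the emergency room sentence removes SAE status from some events that the definition makes serious. The consequence is a missed or late SAE report and a possible undercount of serious TEAEs, not a lost event. Efficacy analyses, sample size and type I error are untouched.

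The conclusion rests on the text alone, and on the assumption that at least some sites would follow the sentence as written. The number of affected events cannot be estimated from the documents.

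A reader might also infer that under-reporting would differ between arms and so bias the safety comparison, with drug-related events lost on fostamatinib and disease-related events lost on placebo. The documents do not support that. They give neither the frequency of affected events by arm nor any information on how sites would classify them.

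**What to change.** Reconcile the two parts of Section 9.1 by replacing the closing sentence of the exclusion list with wording such as: *An emergency room stay shorter than 24 hours, or an admission for social, administrative or travel reasons, does not by itself satisfy the in-patient hospitalization criterion. The underlying event is still an SAE if any other seriousness criterion in this section is met.* Any SAE completion guidance given to sites should carry the same wording.

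This writes down the probable intent and gives these stays the protection already given to pre-planned admissions. The cost is a short edit to one section and probably a few more SAE forms. No endpoint, analysis or clinical management rule changes.
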